### **6.3.2. PGI-C Response**

- Summary: Proportion of subjects with PGI-C response defined as greatly improved or moderately improved at all the timepoints collected.
- Population: Efficacy.
- Statistical Method: For placebo-controlled phase, statistics including number and percentage with 95% confidence interval (based on Clopper-Pearson method) by treatment group, and treatment difference with 95% confidence interval (based on Chan and Zhang's exact method) will be presented. Missing data will be treated as non-responders. Summary based on observed data will also be provided. For TP2 and TP3, descriptive statistics including number and percentage with 95% confidence interval (based on Clopper-Pearson method) will be presented based on observed data.

### **6.4. Other Endpoints**

Not applicable. No pharmacokinetic or pharmacodynamic parameters were evaluated in this study.

### **6.5. Subset Analyses**

No subgroup analyses will be performed.

### **6.6. Baseline and Other Summaries and Analyses**

#### **6.6.1. Baseline Summaries**

Demographics and medical history will be summarized for all participants. Baseline disease characteristics will also be summarized.

#### **6.6.2. Study Conduct and Subject Disposition**

Subjects evaluation, disposition, and discontinuation will be summarized for all participants.

#### **6.6.3. Study Treatment Exposure**

A summary of compliance and the number of doses received as well as the median total dose by visit and groups will be provided. Compliance (%) = (sum of actual number of doses / sum of planned number of doses) \* 100 for each visit period. Where sum of actual number of doses = total duration of each visit period\* actual dose (Tablet) and sum of planned number of doses = total duration of each visit period\* planned dose (Tablet)

Duration of treatment in months will be summarized by the total number of days of dosing, calculated by (last dosing end date - first dosing start date + 1 - number of missed or zero doses days)/ 30.4375..

For a specific dosing record, if the dosing end date is missing and the participant is still in the study, then the CSR cut-off date will be applied.

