7. DISCONTINUATION OF STUDY INTERVENTION AND PARTICIPANT DISCONTINUATION/WITHDRAWAL

7.1. Discontinuation of Study Intervention

7.1.1. Permanent discontinuation

In rare instances, it may be necessary for a participant to permanently discontinue study intervention (ie, definitive discontinuation). Reasons for definitive discontinuation of study intervention include the following: treatment-related SAEs, serious infections, and other events as described in [Section 10.7.2](#).

Note that discontinuation of study intervention does not represent withdrawal from the study. If study intervention is definitively discontinued, the participant will remain in the study to be evaluated for the assessments at the Early Termination (ET) and Follow-up visits (per the SoA [Section 1.3]). See the SoA (Section 1.3) for data to be collected at the time of discontinuation of study intervention and follow-up and for any further evaluations that need to be completed.

In the event of discontinuation of study intervention, it must be documented on the appropriate CRF/in the medical records whether the participant is discontinuing further receipt of study intervention or also from study procedures, posttreatment study follow-up, and/or future collection of additional information.

Refer to Section 10.7 for discontinuation criteria.

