7.1.1.1. Observation Period

Participants will be asked to remain in the study after the Follow-up visit without study intervention. The Period during which participants are in the study after having permanently discontinued study intervention is referred to as the Observation Period. During this period participants will continue to comply with study visit schedules for approximately 2 years or until study end, whichever occurs first. At visits during the Observation Period, only the SALT, PGI-C, and concomitant medications/treatments will be collected at the visits specified in the applicable SoAs in Section 1.3.2; AE and SAE reporting will follow the guidelines in Section 8.3.

Participants will complete the final visit in the Observation Period approximately 2 years after the last dose of study intervention or at study end whichever occurs first as follows:

- at the protocol-scheduled visit 24 months after the last dose of study intervention, OR
- at the next scheduled visit after the 24-month time point (if no scheduled visit falls at the 24-month time point), OR
- at study end.

For example, if the last dose of study intervention occurs around the time of Month 22E then the final visit in the Observation Period would be conducted at Month 51E (ie, the next closest scheduled visit occurring 24 months after Month 22).

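### The SAP's rule for a missing dosing end date tests study status, not treatment status, so it could count untreated Observation Period time as exposure (minor)

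*SAP*

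**What the plan says.** SAP 6.6.3 computes duration of treatment in months from "last dosing end date - first dosing start date + 1 - number of missed or zero doses days)/ 30.4375". It gives one rule for missing dates, which works record by record rather than by participant: "if the dosing end date is missing and the participant is still in the study, then the CSR cut-off date will be applied". Two conditions must both hold: the end date is blank, and the participant has not left the study.

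The protocol separates leaving the study from stopping drug. Section 7.1.1 states: "Note that discontinuation of study intervention does not represent withdrawal from the study". Section 7.1.1.1 adds: "The Period during which participants are in the study after having permanently discontinued study intervention is referred to as the Observation Period". That period ends "at the protocol-scheduled visit 24 months after the last dose of study intervention", at the next scheduled visit after that point, or at study end.

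SAP 8.2 lists duration of treatment among the tables that use the Table 4 groupings in supplemental CSR 1. The Overall column of Table 4 explicitly covers the Observation Period.

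**The concern.** An Observation Period participant is in the study and off drug, and so meets the second condition of the rule by definition. If the end date on that participant's dosing record is also blank, the written instruction extends dosing to the cut-off. The cut-off cannot fall before the true last dose for data in that cut, so any resulting error lengthens exposure, and it does so in people who stopped treatment.

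The version history suggests how this arose. The Observation Period came with protocol Amendment 2. SAP version 5.0 then revised the risk periods in 3.6.1 and added Table 4, but no change to 6.6.3 is listed for version 4.0 or 5.0. Because that table lists major changes only, this is an inference.

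At stake is the accuracy of the exposure summaries that give context to the safety tables in supplemental CSR 1.

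**Working it through.** The plan states no figure on this point, so there is nothing to reproduce. The check applies the SAP 6.6.3 formula with and without the imputed date.

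**Inputs**
- Days per month: 30.4375 (SAP 6.6.3).
- Day 91E is the Month 3E visit and Day 451E the Month 15E visit (Protocol 1.3.2.1). Days marked E count from the start of the active therapy extension phase.
- 30 participants per group (Protocol 9.2).
- Assumed for illustration: last dose Day 91E, cut-off Day 451E, no other missed doses, first dosing day taken as Day 1E. An earlier start in TP1 adds the same amount to both results and leaves the difference unchanged.

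**One participant**
- End date recorded: (91 − 1 + 1)/30.4375 = 2.99 months. The rule does not fire and the excess is 0.
- End date blank, rule as written: (451 − 1 + 1)/30.4375 = 14.82 months. The excess is 360/30.4375 = 11.8 months.
- End date blank, but the 360 off-drug days entered as missed or zero-dose days: (451 − 360)/30.4375 = 2.99 months. The excess is 0.
- A later stop shrinks the error. With last dose on Day 181E, the excess is (451 − 181)/30.4375 = 8.87 months.

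**Outer bound**
The nominal Observation Period is 24 months. In the protocol's own example, dosing ends around Month 22E and "the final visit in the Observation Period would be conducted at Month 51E", which is 29 months. Reaching that length at the CSR 1 cut-off would require the participant to be 36 months ahead of the last participant's Month 15E visit (51 − 15), so about 24 months is the more useful ceiling.

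**Group mean, n = 30, by number k of affected records (k is assumed; the documents do not give it)**

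| k | 11.8 months each | 24 months each |
|---|---|---|
| 0 | 0 | 0 |
| 1 | 11.8/30 = 0.4 | 24/30 = 0.8 |
| 3 | 35.4/30 = 1.2 | 72/30 = 2.4 |

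**Which reports**
- Supplemental CSR 2 is prepared after the last participant has completed the last visit or discontinued (SAP 8.3). Nobody is then still in the study, so the rule cannot fire.
- The PCD-CSR appears to precede the Observation Period in practice: SAP version 4.0, the first under Amendment 2, describes additions to that report in the past tense.
- That leaves mainly supplemental CSR 1.

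**The case against.** The strongest reply is that the rule is an ordinary data-cut convention. People still dosing at a cut-off have no end date yet, and the cut-off is the right value for them. For people who have stopped, the documents presuppose a known last dose:
- Protocol 7.1.1 requires that "it must be documented on the appropriate CRF/in the medical records whether the participant is discontinuing further receipt of study intervention".
- The Early Termination visit is tied to the last dosing day (Protocol 1.3.3).
- The Observation Period is timed from the last dose (Protocol 7.1.1.1).
- The Observation Period risk period in SAP 3.6.1 starts the day after the last dose.

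With an end date on file the rule never fires, and the formula subtracts missed or zero-dose days. This stands as far as frequency goes: the error should be rare. It does not rescue the wording. The rule exists for blank dates, and for an off-drug participant it directs the programmer to the cut-off when a better date should already be on file. Nothing says that untreated Observation Period days are entered as zero-dose days.

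Three stronger readings are tempting, and the documents do not support them.
- *Everyone who stopped drug but stays in the study is over-credited.* The rule also requires a missing end date, and no document shows that any such participant has one.
- *Adverse events after stopping would be counted as on-drug.* SAP 3.6.1 defines the risk periods separately and does not say that the imputed date feeds them. It also gives no fallback for a missing last-dose date, which is reason to settle the point but not evidence of an error.
- *An open TP1 placebo record would run on through active dosing.* This needs a blank TP1 end date to survive the Month 9 cleaning and lock. For someone still dosing at the cut-off, the overall span is unchanged, because it runs from the first start to the last end.

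**Conclusion.** The point holds conditionally and is minor. As worded, SAP 6.6.3 gives an inflated duration of treatment when three things coincide: the participant has permanently stopped drug but remains in the study at the cut-off, a dosing record has no end date, and the untreated days are not entered as missed or zero-dose days. The excess is then the time from true last dose to cut-off: 11.8 months in the example, with a ceiling of about 24 months for the nominal Observation Period. One record at 11.8 months moves a 30-participant mean by about 0.4 months.

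The number of affected records is unknown and probably small. The effect is confined to descriptive exposure summaries, mainly in supplemental CSR 1. The BAEP, biopsy and efficacy results are not touched.

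Study status is also a poor condition for another reason. Protocol 10.7.2 has discontinued participants withdrawn after the Early Termination and Follow-up visits, whereas 7.1.1.1 asks them to remain. Those passages need reconciling. A rule based on treatment status would not depend on the outcome.

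**What to change.** Replace the sentence in SAP 6.6.3. If a dosing end date is missing:
1. Apply the CSR cut-off only if the participant is still on study intervention at the cut-off.
2. Otherwise use the day before the next dosing record starts, where there is one.
3. Where there is none, use the documented last-dose date, with the Early Termination visit date as the latest fallback.

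Step 2 also closes the overlapping-record case. In step 3, an Early Termination visit held within its +7-day window limits the overstatement to about 7/30.4375 = 0.23 months.

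Add one sentence to SAP 3.6.1 stating that any last-dose date used in the risk periods follows the same rule.

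The cost is two SAP sentences and one programming condition. No new data are needed, since the fix relies on dates the protocol already expects to be recorded.

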#### **6.6.4. Concomitant Medications and Non-Drug Treatments**

Prior drug and non-drug treatments, concomitant drug and non-drug treatments will be summarized for all participants.

#### **6.6.5. Alopecia areata history**

Alopecia areata history will be summarized.

- Participants with a SALT score of <100% at Baseline (regardless of the category in the AA history CRF) will be categorized as non-AT/non-AU.
- Participants with a SALT score of 100% at Baseline (regardless of the category in the AA history CRF) will be categorized as AT/AU.
  - Within the AT/AU category, classification into the AT and AU subcategories will be based in the AA history CRF;
  - Participants with a SALT score of 100% at Baseline who were not classified as AT or AU in the AA history CRF are considered as "Not specified".

#### **6.7. Safety Summaries and Analyses**

Safety analysis will be based on the safety population.

Analyses for the primary and secondary safety endpoints are discussed in [Section 6.1](#) and [Section 6.2](#).

In general, safety data will be presented in tabular and/or graphical format and summarized descriptively, where appropriate. All safety endpoints will be listed and summarized in accordance with Pfizer Standards. Categorical outcomes (eg, AEs) will be summarized by subject counts and percentage. Continuous outcome (eg, blood pressure, pulse rate, etc.) will be summarized using N, mean, median, standard deviation, etc. Change from baseline in laboratory data, ECGs and vital signs will also be summarized. Subject listings will be produced for these safety endpoints accordingly. Clinically significant abnormalities in vital signs and clinical laboratory values are discussed in [Sections 6.2.9](#) and [6.2.10](#).

In order to report the impact of COVID-19 on clinical trial populations and study data, additional listings and summaries will be produced:

- Protocol deviations related to COVID-19
- Summary of discontinuations due to COVID-19 related reasons
- Discontinuation from study/study drug interruptions due to COVID-19 related adverse events
- COVID-19 related adverse events
- Number of days with missed doses due to COVID-19
- Missed visits summary for I-V interval latency on BAEP

#### **6.7.1. Adverse Events**

The safety data will be summarized in accordance with CDISC and Pfizer Standards (CaPS). All safety data will be summarized descriptively through appropriate data tabulations, descriptive statistics, categorical summaries, and graphical presentations.

Adjudication data will be reported separately.

#### **6.7.2. Laboratory Data**

Laboratory data will be listed and summarized in accordance with the Pfizer reporting standards. Summaries of subjects meeting pre-specified monitoring and discontinuation criteria will be created using methods for categorical data.

#### **6.7.3. Vital Signs**

Vital signs will be summarized at baseline and all-available post-baseline visits.

Height will be collected pre-dose and weight will be collected at pre and post dose.

#### **6.7.4. Electrocardiogram**

ECG parameters QTcF and change from baseline will be summarized at baseline and all available post-baseline visits. Categorization of QTcF will also be provided.

## 7. INTERIM ANALYSES

There is no formal interim analysis planned in this study. However, if required, interim analyses may be performed for study monitoring for internal decision making, due to regulatory requests, or to support regulatory submissions. As no statistical hypotheses will be tested in this study, there are no issues of protecting the Type I error rate.

This study uses an External Data Monitoring Committee (E-DMC). The E-DMC will be responsible for ongoing monitoring of safety of subjects in the study according to the DMC charter. The recommendations made by DMC to alter the conduct of the study will be forwarded to the appropriate Pfizer personnel for final decision. Pfizer will forward such decisions, which may include summaries of aggregate analyses of safety data, to regulatory authorities, as appropriate.

Independent safety adjudication committees will be used for opportunistic infections, cardiovascular events, neurological, including audiological events, and malignancy events.

## 8. TIMING AND TREATMENT GROUPS DISPLAYED FOR EACH ANALYSIS

There will be 3 Clinical Study Reports (CSRs) for this study: one PCD-CSR, and two supplemental CSRs.

### 8.1. PCD-CSR

The PCD-CSR will include the primary analysis for this study, which will be conducted following the PCD at Month 9 (TP1), and after the Month 9 data are cleaned and locked for all participants. The following data will be included:

- Efficacy data through Month 9 (TP1)
- All safety data collected through the PCD data cut-off date

For duration of treatment, concomitant medication, lab abnormality, lab values meeting discontinuation criteria, vital signs/QTcF values meeting pre-specified criteria and AE tables, the following groups will be summarized:

**Table 3. Groups**

Period	Groups
Placebo-controlled phase (TP1)	
 
• Ritlecitinib 200/50 mg QD
 
• Placebo
 

Active therapy extension phase (TP2)	
 
• Ext Ritlecitinib 50 mg QD
 
• Ext Ritlecitinib 200/50mg QD
 

Overall (TP1+TP2)	
 
• Ritlecitinib 200/50/50 mg QD
 
• Any Ritlecitinib
 
• Any Ritlecitinib + Placebo (Total)
 

For tables summarizing data by visit (such as BAEP, skin punch biopsy endpoints and efficacy endpoints), which only include data from TP1 in the PCD-CSR, the following groups will be summarized:

- Ritlecitinib 200/50 mg QD
- Placebo

For other tables such as dispositions, demographic and baseline characteristics, medical history, primary diagnosis, prior medications and compliance the groups to be summarized will be:

- Ritlecitinib 200/50 mg QD
- Placebo → Ritlecitinib 200/50 mg QD.

## 8.2. Supplemental CSR 1

The supplemental CSR 1 will be prepared after the last participant completes the 4-week follow-up visit, or the Month 15E visit (TP2) if the last participant is enrolled in TP3, whichever is later. This CSR will include:

- Efficacy through Month 15E (TP1+TP2). Efficacy data from participants while they are on the Observation Period will not be included in the summaries of efficacy. Instead, listings and plots may be provided.
- All safety data collected through the cut-off date for this CSR (including the Follow-up Period and the Observation Period).

For summaries in this CSR, the groups will be the following:

- For duration of treatment, concomitant medication, lab abnormality, lab values meeting discontinuation criteria, vital signs/QTcF values meeting pre-specified criteria and AE tables.

**Table 4. Groups**

Period	Groups
Placebo-controlled phase (TP1)	
 
• Ritlecitinib 200/50 mg QD
 
• Placebo
 

Active therapy extension phase (TP2)	
 
• Ext Ritlecitinib 50 mg QD
 
• Ext Ritlecitinib 200/50mg QD
 

Overall (TP1+TP2+TP3+Observation period)	
 
• Ritlecitinib 200/50/50 mg QD
 
• Any Ritlecitinib
 
• Any Ritlecitinib + Placebo (Total)
 

- For all the other tables, groups will be:
  - Ritlecitinib 200/50/50 mg QD
  - Placebo → Ritlecitinib 200/50 mg QD.

### 8.3. Supplemental CSR 2

The supplemental CSR 2 will be focused on safety and efficacy data from TP3 and will be prepared after the last participant completes the last visit or discontinues from the study.

- Disposition date of TP2 (or of 4 weeks follow-up period if participants didn't enter TP3) will be used to identify records in TP2 and TP3.
- All safety data in TP3, regardless of whether participants are in the Observation Period or not, will be included in summary tables.
- Only one group “All participants” including all participants will be used in all summaries.
- Efficacy data of participants while in the Observation Period will not be included in summary tables that present TP3 data by visit. Instead, listings and plots may be provided.

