  - For patients who entered in TP3, RP is defined from date of 1st dose in TP3 to min (last contact date, last dose date + 35) where last contact date is max (date of discontinuation of study, date of subject's last visit). In the case of an interim data cut, the last contact date is min (date of discontinuation of study, date of data cut-off). If a subject dies, the death date will be the last contact date. This RP includes AEs that occur within 35 days after the last dose
- The following RP will be applied for Observation Period for patients who entered from TP3
  - For patients who entered the observation period from TP3, RP is defined from date of last dose + 1 to last contact date, where last contact date is max (date of discontinuation of study, date of subject's last visit). In the case of an interim data cut, the last contact date is min (date of discontinuation of study, date of data cut-off). If a subject dies, the death date will be the last contact date. This RP excludes AEs starting while on-drug.
- Supplemental CSR1 will include summaries of TEAEs as described in [Table 4](#).
- Supplemental CSR2 will include summaries of TEAEs for the RP defined for TP3, and for the RP defined for the Observation period for patients who entered from TP3.

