## 11. APPENDICES

### 11.1. Appendix 1 Definition and Use of Visit Windows in Reporting

Visit windows will be used for efficacy variables and for any safety data that are displayed or summarized by study visit.

Visit Label	Target Day	Analysis Visit Window
Baseline	1	Up to Day 1
Month 1	31	Days 2 to 60
Month 3	91	Days 61 to 136
Month 6	181	Days 137 to 226 but <=Day 1E
Month 9	271	Days 227 to 316 but <=Day 1E
Month 3E	91E	Days 2E to 136E
Month 6E	181E	Days 137E to 226E
Month 9E	271E	Days 227E to 316E
Month 12E	361E	Days 317E to 406E
Month 15E	451E	Day 407E to 541E
Month 21E	631E	Day 542E to 721E
Month 27E	811E	Day 722E to 901E
Month 33E	991E	Day 902E to 1081E
Month 39E	1171E	Day 1082E to 1261E
Month 45E	1351E	Day 1262E to 1441E
Month 51E	1531E	Day 1442 to last dose + 14 days
28-Day Follow-up	28 days after last dose	Based on nominal visit
6-Month Follow-up	182 days after discontinuation	Based on nominal visit

E=relative day to the first dose at active therapy extension phase.

If more than one observation falls within a visit window, the observation that is the closest to the target date for that visit will be used for the summary tables. If two visits are equally distant from the target day, the data from the later visit will be used.

Data collected in TP2, from the first dose in TP2 till the end of follow-up or the first dose in TP3, will be used to derive analysis visits in TP2. Data collected in TP3, from the first dose in TP3 or the Observation Period will be used to derive analysis visits in TP3.

Some endpoints (eg, BAEP) are not scheduled to be assessed at each visit and some measurement may fall outside the scheduled visit windows. In this case, for variables where mixed model methodology is used, the data from the unscheduled 'windowed' visits will not be included in mixed model analysis. However, these visits will be summarized descriptively in the observed cases analysis, using the visit timepoint corresponding to their actual visit window (for example a participant with a visit on Day 59 will be summarized at Month 1 in the observed case summaries).

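### SAP 8.3 and SAP 3.6.1 give incompatible rules for which safety records count as TP3 data in supplemental CSR 2, and 3.6.1 leaves the Observation-from-TP2 risk period without a TEAE summary after the CSR 1 cut-off

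*SAP*

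**What the plan says.** **SAP 8.3 (Supplemental CSR 2)** sets three rules for safety data.
- Sorting: "Disposition date of TP2 (or of 4 weeks follow-up period if participants didn't enter TP3) will be used to identify records in TP2 and TP3".
- Content: "All safety data in TP3, regardless of whether participants are in the Observation Period or not, will be included in summary tables".
- Display: a single group, "including all participants will be used in all summaries".

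**SAP 3.6.1 (Adverse Events)** works with risk periods instead.
- The TP3 risk period belongs to patients who entered TP3. It runs from first TP3 dose to the earlier of last contact and last dose + 35 days.
- Observation entered from TP2 and Observation entered from TP3 each have their own risk period, from last dose + 1 day to last contact.
- CSR 2 is to summarize TEAEs for the TP3 risk period and "for the RP defined for the Observation period for patients who entered from TP3". Observation entered from TP2 is not listed.

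**SAP 8.2** limits CSR 1 to safety data up to that report's cut-off, Observation Period included.

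**SAP Appendix 1 (11.1)**, on visit windows, says: "Data collected in TP3, from the first dose in TP3 or the Observation Period will be used to derive analysis visits in TP3".

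**The concern.** Two sections of one SAP govern the same CSR 2 tables and send the same records to different places. Under 8.3, a participant who stopped drug in TP2 and stayed for observation can supply TP3 safety records, and possibly a place in the denominator, without a TP3 dose. Under 3.6.1, that participant has a defined off-drug risk period, but once CSR 1 has closed no TEAE summary is assigned to it.

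The safety statistic is a plain number and percentage of subjects (SAP 6.2.6), so who counts as a TP3 participant moves the result directly. This is a safety study of about 60 people, and a few reassigned participants would be visible in a percentage. Those observed from TP2 are also not a random subset: protocol 7.1.1 names treatment-related SAEs and serious infections among the reasons for permanent discontinuation.

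**Working it through.** The plan states no figure on this point, so the check sets the rules side by side and then looks at how much data they could affect.

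**1. Where each record goes**

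| Record | SAP 3.6.1 | SAP 8.3 read literally |
|---|---|---|
| TP3 entrant, event between first TP3 dose and last dose + 35 days | TP3 risk period, summarized in CSR 2 | TP3 |
| TP3 entrant, event more than 35 days after last dose | Observation-from-TP3, its own period in CSR 2 | TP3 tables; no on-drug/off-drug split stated |
| Stopped in TP2, no TP3 dose, event after the 4-week follow-up disposition date | Not TP3; Observation-from-TP2 | TP3 record, all-participants group |
| Same person, event after the CSR 1 cut-off | Risk period defined; CSR 1 closed; not listed for CSR 2 | TP3 record, in CSR 2 |

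Only the first row agrees. In rows three and four, the 8.3 sorting rule names just two destinations, TP2 and TP3. For someone who never entered TP3 it says when TP2 ends, so anything later falls to TP3.

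**2. Overlap between risk periods**

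The TP2 period ends at last dose + 35 and the Observation-from-TP2 period starts at last dose + 1. They share 35 − 1 + 1 = 35 days, and an event in those days meets both definitions. The TP3 and Observation-from-TP3 periods overlap in the same way.

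**3. How much AE collection falls after the CSR 1 cut-off**

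Protocol 7.1.1.1 limits Observation visits to SALT, PGI-C and concomitant treatments, with AEs handled under protocol 8.3. Protocol 8.3.1 gives two ends to active collection: a minimum of 28 days after last dose, or Visit 19 (182 ± 30 days, protocol 1.3.3). The documents give no cut-off date, so let L be an assumed lag in months from last dose to cut-off. With 30.4375 days per month (SAP 6.6.3):

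remaining months = max(0, days / 30.4375 − L)

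| L (assumed) | 28 days | 182 days | 212 days |
|---|---|---|---|
| 1 | 0 | 5.0 | 6.0 |
| 3 | 0 | 3.0 | 4.0 |
| 6 | 0 | 0 | 1.0 |
| 12 | 0 | 0 | 0 |

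**4. Effect on a percentage (assumed counts only)**

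Let e be on-drug events, n participants dosed in TP3, m participants observed from TP2, and k off-drug events among those m. The 3.6.1 set gives e/n. The literal 8.3 set gives (e + k)/(n + m).

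| n | m | e | e/n | k = 0 | k = 1 |
|---|---|---|---|---|---|
| 50 | 5 | 5 | 10.0% | 5/55 = 9.1% | 6/55 = 10.9% |
| 50 | 10 | 5 | 10.0% | 5/60 = 8.3% | 6/60 = 10.0% |
| 40 | 5 | 5 | 12.5% | 5/45 = 11.1% | 6/45 = 13.3% |
| 40 | 10 | 5 | 12.5% | 5/50 = 10.0% | 6/50 = 12.0% |

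The percentage can fall, stay level or rise.

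**The case against.** The best defence is that 3.6.1 is the specific rule for AEs and already keeps TP3 and Observation apart. On that view the single group in 8.3 is only a display column replacing the by-arm columns of Table 4, and no untreated person enters a TP3 TEAE denominator. This is a reasonable reading, but 8.3 does not state it. Its instruction covers all safety data and makes no exception for AEs, so a programmer could follow either section.

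Several stronger inferences do not stand:

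- **That late events are lost.** A reader of 3.6.1 alone might conclude that events after the CSR 1 cut-off in people observed from TP2 are never reported. SAP 8.3 would bring them into CSR 2, and SAP 6.7 provides subject listings. What is missing is an assigned TEAE summary under 3.6.1.
- **That up to two years of AE data are at stake.** The Observation Period lasts about 2 years after the last dose, but active AE collection ends far sooner, as step 3 shows. Protocol 10.7.2, which has participants meeting discontinuation criteria withdrawn after the Early Termination and Follow-up visits, may shrink the group further. Investigators must still report related SAEs they learn of later (protocol 8.3.1), so the number is not necessarily zero.
- **That Appendix 1 contradicts 8.3.** It starts TP3 visits at the first TP3 dose for entrants but also maps Observation Period data to TP3 visits. It is closer to 8.3 and itself needs aligning with 3.6.1.
- **That Table 4 is an error because its Overall columns include the Observation Period.** The label says so and the version history for SAP 5.0 records it. The columns are descriptive, TP1 and TP2 are shown separately, and both TP1 arms share one risk-period rule, so the randomized comparison is unaffected. It is a documented choice.

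**Conclusion.** The conflict is real and should be settled before CSR 2 is programmed. Followed literally, 8.3 counts records from people with no TP3 dose as TP3 safety data. Followed literally, 3.6.1 leaves a risk period that it defines without a TEAE summary after the CSR 1 cut-off. The 35-day overlap and Appendix 1 belong to the same repair.

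The practical size is probably small. Scheduled Observation visits add no laboratory, vital-sign or ECG data. Depending on which end of AE collection applies, between 0 and about 6 months of active collection fall after the cut-off for an assumed lag of 1 month or more. The documents do not say how many participants are in Observation from TP2, so the percentage shifts in step 4 rest on assumed counts and have no fixed direction. A reader might infer a systematic dilution of TP3 incidence; the text does not support that. The primary BAEP analysis and the TP1 comparison are not touched.

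**What to change.** 1. In SAP 8.3, base TP3 TEAE and other safety summaries on participants with at least one TP3 dose, over the TP3 risk period already defined in 3.6.1. For these tables this replaces the disposition-date rule.
2. In SAP 3.6.1 and 8.3, add the Observation-from-TP2 risk period, through study end, to the CSR 2 TEAE summaries. Show it apart from TP3 and beside Observation-from-TP3, each with its own denominator.
3. In Appendix 1, align the mapping of Observation Period data to TP3 visits with these rules for safety data.
4. Assign the 35-day overlap between the on-treatment and Observation risk periods to one period.

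Table 4 can stay as it is. The cost is SAP wording, a period flag in the analysis data, and an added Observation display in CSR 2. No data collection changes.
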